Study Protocol and Statistical Analysis Plan

(Version: 2.0 Date: 2023.3.28)

Name: Construction of Symptom Network in Maintenance Hemodialysis Patients

Applicant: Ren Ji Hospital, Shanghai Jiao Tong University School of Medicine

Principal investigator: [name]

Objective

Through a cross-sectional questionnaire survey, a general information questionnaire and Dialysis Frequency, Severity, and Symptom Burden Index were used to investigate the frequency, severity, and degree of symptom distress in MHD patients, and to analyze the differences in symptom distress status between long and short dialysis age MHD patients. Using the R 4.2.2 software qgraph package, construct symptom networks for MHD patients of long and short dialysis age through network analysis. Analyze network centrality indicators, including intensity, closeness centrality, and mediation centrality, to identify core symptoms and compare if there are any differences between the two groups, aiming to lay the foundation for precise and efficient phased symptom management.

Background

End stage renal disease (ESRD) is caused by various kidney diseases, leading to irreversible decline in renal function. The main renal replacement therapy (RRT) for ESRD is hemodialysis (HD), peritoneal dialysis (PD), and kidney transplantation. Due to the impact of kidney supply on kidney transplantation, it is limited in clinical practice, and hemodialysis has become the most common method of RRT in most countries. According to the registration system of the Chinese Research Data Services (CNRDS), as of the end of 2021, there were 751098 dialysis patients and 155738 new patients in China, with an average dialysis age of 50.9 months. The proportion of patients with dialysis age greater than 5 years was 31.5%. There are a large number of hemodialysis patients with a longer dialysis age.

With the continuous development of dialysis technology, the survival rate of maintenance hemodialysis (MHD) patients is becoming higher and higher. However, MHD patients may experience various symptoms during long-term treatment, which is the main cause of discomfort and physical and mental health for patients. The physical and mental pain or torment experienced by patients due to the disease itself and/or the symptoms caused by treatment is called symptom distress. Multiple studies have shown that the incidence of symptom distress in MHD patients ranges from

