management measures for depression in clinical practice. Han et al. constructed symptom networks for autism and schizophrenia. Yang Hongli et al. applied symptom networks to HIV infected individuals and identified fatigue as the core symptom. They suggested that when HIV infected individuals have multiple symptoms at the same time, high-intensity and precise intervention on fatigue can reduce the transmission of fatigue as a mediating bridge in the symptom network, reduce the severity of fatigue symptoms, and also alleviate the severity of other symptoms. As mentioned above, symptom network analysis can identify core symptoms, and changing these core symptoms may be an important entry point for changing the entire network. In practical clinical work, implementing key interventions by nurses on core symptoms can more effectively improve other related symptoms and improve intervention efficiency. Applying symptom networks to the field of symptom management is a promising and precise technology in real-world clinical settings.

This study has developed a symptom distress questionnaire for maintenance hemodialysis patients. Previous literature on symptom distress and symptom management in MHD patients has been reviewed. Whether there are differences in symptom distress among MHD patients of different dialysis ages, and how to identify the core symptoms of MHD patients of different dialysis ages through symptom networks to improve the accuracy and effectiveness of intervention are all directions that need to be studied in the future. The research hypotheses of this study are: ① There are differences in the frequency, severity, and degree of symptom distress between long and short dialysis age MHD patients; ② By using network analysis methods to construct symptom networks for long and short dialysis age MHD patients, identify the core symptoms of different dialysis age MHD patients. Based on literature review and clinical experience, it is assumed that the core symptoms of long dialysis age MHD patients are itching or dry skin, while the core symptoms of short dialysis age MHD patients are fatigue or dry mouth.

Contents

1. Current survey of symptom burden in maintenance hemodialysis patients

① Understanding the current status of symptom distress in maintenance hemodialysis patients through cross-sectional questionnaire survey

② Comparative analysis of symptom distress in maintenance hemodialysis patients with long and short dialysis age

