2. Construction of symptom network and core symptom recognition for maintenance hemodialysis patients

① A multicenter study on the current status of symptom distress in maintenance hemodialysis patients

② Construct symptom networks for long-term, short-term, and all maintenance hemodialysis patients using network analysis based on cross-sectional survey data from multiple centers

③ Identify and analyze the core symptoms of long dialysis age, short dialysis age, and all maintenance hemodialysis patients based on network centrality parameters

Methods

Participants

Convenient sampling method was used to select MHD patients from six blood purification centers, including the East, West, South, Baoshan Branch, Ningbo Hangzhou Bay Branch, and Punan Hospital of Renji Hospital Affiliated to Shanghai Jiao Tong University School of Medicine.

(1) Inclusion criteria: ① Age not less than 18 years old; ② Regular hemodialysis time greater than or equal to 3 months; ③ The dialysis plan did not change within one month; ④ Informed consent and voluntary participation in this study.

(2) Exclusion criteria: ① Previous or current mental illness; ② Cognitive impairment; ③ Acute cardiovascular and cerebrovascular disease; ④ Acute infection period; ⑤ Complications such as severe cerebrovascular sequelae and tumors.

(3) Sample size and calculation method: The Dialysis Frequency, Severity, and Symptom Burden Index for dialysis patients used in this study includes a total of 30 symptoms. When constructing a symptom network model, the threshold parameters

that need to be estimated are 30, paired association parameters are $30 \times \frac{(30-1)}{2} = 435$, and the total parameters are $30 + 435 = 465$. Therefore, the sample size needs to be at least 465. Considering 10% of invalid samples, the sample size of this study is at least $465 \div (1 - 10\%) = 517$.

Instruments

General Information Questionnaire: Designed by the researchers themselves, including laboratory examination indicators such as gender, age, dialysis age, marital status, educational level, work status, residential status, medical expense payment method, economic burden, primary disease, comorbidities, recent medication, hemoglobin, etc.

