Enter the collected information into the database established by Epidata 3.1, and after verification, import it into SPSS 21.0 software for data analysis. The patient's gender, marital status, education level, work status, and other counting data are described using frequency and percentage. Age, hemoglobin, blood phosphorus, and other measuring data that meet normality are represented by mean and standard deviation, while those that do not meet normality are represented by median and interquartile spacing. The symptom distress scores of MHD patients with different characteristics were tested for normality and homogeneity of variance. If they obey the normal distribution and have the same variance, t-test and analysis of variance were used. Otherwise, nonparametric rank sum test was used. Use R4.2.2 software qgraph package for network analysis to generate complex network descriptions of the relationship between symptoms. Use network centrality indicators such as strength, tight centrality, and mediation centrality to represent the degree of interconnection of symptom networks. The intensity reflects the total direct connection between symptoms and other symptoms, that is, the ability of symptoms to affect other symptoms; The closeness centrality reflects the reciprocal of the distance between symptoms and other symptoms, that is, the core position of symptoms in the network; Mediation centrality reflects the number of shortest paths through the symptom, which serves as a bridge between the symptoms in the network.

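### Core symptoms are to be named from centrality indices that ignore the sign of a link, with no deciding index, although their intended use requires positive links

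*Combined protocol and SAP*

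**What the plan says.** The Objective sets the task: "Analyze network centrality indicators, including intensity, closeness centrality, and mediation centrality, to identify core symptoms". Contents, item 2, repeats it for the long dialysis age, short dialysis age and all-patient networks; core symptoms are to be identified "based on network centrality parameters". The Statistical Analysis Plan section gives the same list: "Use network centrality indicators such as strength, tight centrality, and mediation centrality".

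That section describes strength as follows: "The intensity reflects the total direct connection between symptoms and other symptoms", glossed as "that is, the ability of symptoms to affect other symptoms". The notion of a core position is attached to closeness instead: "that is, the core position of symptoms in the network". Betweenness (there called mediation centrality) is described as a bridging role.

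On estimation the section says only "Use R4.2.2 software qgraph package for network analysis". It does not say whether edges are correlations, partial correlations or regularised partial correlations. No signed index is listed, negative edges are not mentioned, and no rule says which index decides when the three disagree.

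The Background gives the reason for finding a core symptom: "implementing key interventions by nurses on core symptoms can more effectively improve other related symptoms".

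**The concern.** The Background's use of a core symptom has a direction: reduce it, and its neighbours should fall too. A negative edge means that more of one symptom goes with less of another, so it counts against that use. Strength in its standard form adds absolute edge weights, so a negative edge raises the score as much as a positive edge of the same size. Standard closeness and betweenness also work from absolute weights. None of the three planned indices can therefore separate supporting links from opposing ones.

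There are two routes to a misleading result. Real negative links may exist. Or all real links may be positive, while sampling error makes many weak or absent edges come out slightly negative; an unsigned sum then counts that noise as connection. The core symptoms are proposed as targets for nursing intervention, so naming the wrong one would misdirect later work.

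**Working it through.** **The plan's own figure.** Methods, sample size: 30 symptoms give 30 × 29 / 2 = 435 pairs; 30 + 435 = 465; 465 / 0.9 = 516.7, rounded up to 517. This reproduces. The choice of index does not enter it.

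**Definitions.** For symptom i with edge weights w_ij to the other 29 symptoms:
- strength_i = Σ_j |w_ij|
- expected influence_i = Σ_j w_ij
- strength_i − expected influence_i = 2 × (sum of the absolute values of the negative edges at i)

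The two are identical for a symptom with no negative edges. They separate by twice the negative weight otherwise.

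**Group sizes used for illustration.** The plan sizes only the total. The Background's national share with dialysis age over 5 years is 31.5%. Applied to 465, this gives 0.315 × 465 ≈ 146 long and 465 − 146 = 319 short. This split is an assumption; six centres sampled by convenience may differ.

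**Noise alone.** In an unregularised partial-correlation network with no true edges, an estimated edge has standard deviation of about 1/√(n − 30 + 1). Expected strength per symptom is then 29 × √(2/π) / √(n − 29):
- n=465: 23.14 / √436 = 1.11
- n=319: 23.14 / √290 = 1.36
- n=146: 23.14 / √117 = 2.14

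Half of each figure comes from negative edges. In the signed sum the positive and negative noise cancels on average.

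**Simulation.** Assumptions, none of them in the documents: 30 symptoms, 15% of edges present, raw weights 0.05 to 0.30, normal data; 200 data sets per setting, or 40 for EBIC graphical lasso. Right means that the index's top symptom is the top symptom by the true signed sum. Cells show percentages: same top symptom by both indices / strength right / expected influence right.

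| Estimator | n | True links all positive | 10% of true links negative |
|---|---|---|---|
| Unregularised partial correlation | 465 | 40 / 41 / 56 | 35 / 40 / 60 |
| | 319 | 36 / 34 / 53 | 30 / 27 / 47 |
| | 146 | 17 / 14 / 33 | 19 / 17 / 33 |
| Plain correlation | 465 | 92 / 65 / 65 | 62 / 51 / 59 |
| | 319 | 88 / 56 / 52 | 65 / 45 / 48 |
| | 146 | 78 / 46 / 46 | 59 / 40 / 45 |
| EBIC graphical lasso | 465 | 100 / 57 / 57 | 80 / 65 / 70 |
| | 319 | 100 / 33 / 33 | 85 / 38 / 38 |
| | 146 | 100 / 23 / 23 | not completed |

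With all-positive truth, negative edges supply 30%, 33% and 37% of total strength (n=465, 319, 146) for unregularised partial correlations, 6%, 9% and 15% for plain correlations, and 0% for EBIC graphical lasso.

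The simulation standard error near 50% is √(0.25/200) = 3.5 points for 200 data sets and √(0.25/40) = 7.9 points for 40. In at least one regularised data set all centrality values were equal, as happens when no edge is retained; agreement there is trivial.

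**Sensitivity to the assumed network.** Unregularised partial correlations, all true links positive, n=465:
- Densities of 15% to 50%, continuous and 5-level ordinal data: expected influence right in 48% to 67%, strength in 16% to 55%.
- A separate set of densities and edge sizes, normal data: 43% to 68% against 13% to 47%. At 25% density within this set: 63% against 36%, falling to 58% against 23% at n=319 and 39% against 10% at n=146.

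The direction is the same throughout; the size of the gap varies widely.

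**The case against.** **The plan does not rank by strength.** A reader might infer that it does, because strength is listed first and is glossed as the ability to affect other symptoms. The text does not support this: three indices stand side by side without priority, and core position is attached to closeness. The text also does not say that signs are dropped; that follows from the standard definitions. Both corrections stand, but they do not remove the mismatch, since all three indices are unsigned in standard form. They do mean that swapping out strength alone would not be enough.

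**The noise argument needs an estimator that the plan does not name.** This stands. The large gap appears only for unregularised partial correlations. The sample size section counts 435 pairwise parameters, which leaves such a network open but does not establish it. That section also counts threshold parameters, which may point to a binary or ordinal pairwise model; no such model was simulated.

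**Negative true links are an assumption, and the benchmark favours the signed index.** Nothing in the documents suggests that 10% of links are negative, and all items are scored so that higher means worse. Where negative links are assumed, some disagreement is only a difference of definition. Still, expected influence did about as well as strength or better in most settings when judged by true strength, and the all-positive results do not depend on negative links at all.

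**A signed sum has its own weakness.** Positive and negative links can cancel and hide a well-connected symptom. The Statistical Analysis Plan section also says that the indices describe interconnection, which unsigned indices do. This is a reason to keep them in the report, though not to let them decide which symptom is core.

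**Conclusion.** The point holds in limited form, as a cheap improvement. The planned indices do not match the plan's stated use of a core symptom, and nothing in the plan says how negative edges are treated or which index decides.

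The size depends on the estimator. With unregularised partial correlations and all true links positive, expected influence finds the true top symptom clearly more often than strength: about 50% to 65% against 15% to 55% at n=465 under assumed settings, and both are lower in smaller groups. With EBIC graphical lasso and all-positive links nothing is gained or lost; with 10% negative links the two agree in 80% (n=465) and 85% (n=319) of samples. With plain correlations neither is clearly better.

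A reader might infer that expected influence is always at least as good. The results do not show that: with plain correlations and all-positive links at n=319 it was right in 52% against 56%, a gap within simulation error. Nor does a signed index show that relieving one symptom relieves another; in cross-sectional data it remains an association. Core symptoms are a main output but not the only one, since the plan also compares symptom frequency, severity and distress between the groups.

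**What to change.** In the Statistical Analysis Plan section:
- Name one-step expected influence, the sum of signed edge weights, as the index that ranks core symptoms in the long dialysis age, short dialysis age and all-patient networks.
- Report strength, closeness and betweenness beside it as descriptions, so that any cancelling of positive and negative links is visible.
- Report the number and size of negative edges in each network.
- State the edge estimator, because the practical weight of this point depends on it.

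The cost is a few sentences. qgraph returns expected influence as well as strength, no new data are needed, and 517 stands. Where no estimated edge is negative, expected influence and strength give the same ranking.

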13.75% to 91.5%, which is at a high level. Symptom distress is negatively correlated with the quality of life of MHD patients. Excessive symptom distress increases the cost of treatment and exacerbates the psychological burden on patients. Persistent symptom burden can significantly affect the quality of life of MHD patients and increase their mortality rate. MHD patients suffer from multiple symptoms at the same time. Li Jiuhong et al.'s research results show that MHD patients experience a total of 3-25 (13.12 ± 5.27) symptoms, which is similar to Weisbord et al.'s average of 9 symptoms. MHD patients experience a wide variety of symptoms, and how to accurately and effectively manage symptoms is the future research direction.

With the prolongation of dialysis treatment time for patients, some urea toxin that cannot be completely cleared by dialysis accumulates in the patient's body, which is closely related to discomfort symptoms such as itching, joint pain, and difficulty falling asleep. Ran Yuli et al. found that the dialysis age of MHD patients is negatively correlated with their physical function and role. With the prolongation of dialysis age, the physiological function of MHD patients will decrease to varying degrees, and various disease-related complications will also occur. The focus of symptom management will shift accordingly. Conducting grouping studies based on dialysis age for MHD patients has certain clinical significance. At present, domestic scholars use a 5-year hemodialysis period as the boundary, dividing dialysis age >5 years into long dialysis age, and dialysis age ≤ 5 years into short dialysis age. Hu Qian and others set up symptom management consultants to develop symptom management pathways and guide responsible nurses to implement symptom management for patients according to the pathway table. The results indicate that setting up symptom management consultants can reduce the incidence of symptoms in MHD patients, improve their quality of life, and improve patient satisfaction. A meta-analysis showed that aerobic exercise can improve several symptoms related to hemodialysis in adults receiving MHD, including restless leg syndrome, depressive symptoms, muscle spasms, and fatigue. Zhao Ying et al. used air wave pressure therapy to prevent dialysis related muscle spasms, Zuo et al. managed symptoms of fatigue through nurse led non drug multidisciplinary holistic care, Beerappa et al. improved sleep

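### If a symptom is left unconnected in one of the three networks, closeness computed as 1/(sum or mean of distances) is 0 for all 30 symptoms there; the plan should define it as a sum of reciprocals

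*Combined protocol and SAP*

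**What the plan says.** The Statistical Analysis Plan section assigns the network analysis to the qgraph package in R 4.2.2 and lists three centrality indices: strength, closeness and betweenness (called mediation centrality). Closeness is described in words only: "The closeness centrality reflects the reciprocal of the distance between symptoms and other symptoms, that is, the core position of symptoms in the network".

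Contents, item 2 ③, sets the use of these indices: "Identify and analyze the core symptoms of long dialysis age, short dialysis age, and all maintenance hemodialysis patients based on network centrality parameters". The Objective adds a comparison between the two dialysis-age groups. The instrument "includes a total of 30 symptoms", so each of the three networks has 30 nodes.

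The document gives no closeness formula. It does not say whether distances are summed, averaged or inverted one by one, what happens to a symptom with no links, or which edge estimator is used.

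**The concern.** The usual way to turn the plan's sentence into a number is to add or average a symptom's distances to all the others and take the inverse. A symptom that cannot be reached lies at infinite distance. Every other symptom then has an infinite total, and its closeness is 0 however well it is linked to the rest.

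Of the three indices, closeness is the one that the plan ties by its wording to being central in the network. If one group's network is connected and the other's is not, one group has 30 usable values and the other has 30 zeros. The planned comparison then has nothing to work with on this index.

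**Working it through.** **1. The plan's own figures.** From Participants, (3) Sample size: 30 × 29 / 2 = 435 pairwise associations; 435 + 30 thresholds = 465; 465 / (1 − 0.10) = 516.7, rounded up to 517. These reproduce. They do not bear on closeness, except that all 435 associations are counted and no pruning of edges is mentioned.

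**2. The algebra.** Let d(i,j) be the shortest-path distance, with edge length 1/weight (an assumption; the plan does not define distance).

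- Sum form: C(i) = 1 / Σ d(i,j). If one d(i,j) is infinite, C(i) = 0.
- Mean form: C(i) = 29 / Σ d(i,j), which is also 0.
- Sum of reciprocals: H(i) = Σ 1/d(i,j). An unreachable symptom adds 0 and the other terms remain.

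An isolated symptom is unreachable from each of the other 29 and reaches none itself, so the first two forms give 0 for all 30.

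**3. Numerical illustration.** A 30-node weighted network with one node cut off:

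| Definition | Symptoms at 0 | Can the rest be ranked? |
|---|---|---|
| 1/(sum of distances) | 30 of 30 | no |
| Sum of 1/distance | 1 of 30 | yes, all 30 values distinct |
| 1/(sum) within the 29 linked symptoms | 0 of 29 | yes, all 29 values distinct |

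Over the 29 linked symptoms, the last two definitions have a Spearman correlation of 0.98. Strength is 0 only for the isolated symptom.

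**4. Can an unconnected symptom occur?** The plan fixes no group split. As an assumption, the national 31.5% with more than 5 years of dialysis (Background) applied to 465 gives 0.315 × 465 = 146.5 long and 318.5 short.

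*Without sparsity:* unregularised partial correlations, one symptom truly independent of the other 29, 200 data sets at each of n = 465, 319 and 146. There were no exactly zero edges and no zero closeness values in any of the 600.

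*With edges pruned at random to density q:* the expected number of isolated symptoms is 30 × (1 − q)^29. The last column comes from 2,000 simulated graphs per density.

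| Density | Expected isolated | Chance of at least one |
|---|---|---|
| 5% | 6.78 | about 100% |
| 10% | 1.41 | 74% |
| 15% | 0.27 | 24% |
| 20% | 0.05 | 4% |
| 25% | 0.01 | 1% |

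*With an EBIC-tuned graphical LASSO:* scores 0–4 and, unless stated, five symptom clusters. Symptom prevalences of roughly 14–90% were assumed in the 20- and 40-sample runs. Entries are networks that were not fully connected; they do not separate partly linked from empty networks except where marked.

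| Assumed setting | n = 147 | n = 318 | n = 465 |
|---|---|---|---|
| Tuning 0.5, mean r 0.21 or 0.28, 20 samples | empty | 75–80% | 5–20% |
| Tuning 0.5, mean r 0.19 or 0.25, 40 samples | 40/40 | 7–16/40 | 0–1/40 |
| Tuning 0.5, mean r 0.28, 10 samples | empty | 10% | not run |
| Tuning 0.5, mean r 0.21 or a single factor, 10 samples | empty | 100% | not run |
| Tuning 0.25, mean r 0.19 or 0.25, 40 samples | 33–38/40 | 0/40 | 0/40 |
| Tuning 0, mean r 0.21 or 0.28, 20 samples | 0–15% | 0% | 0% |
| Tuning 0, mean r 0.19 or 0.25, 40 samples | 0/40 | 0/40 | 0/40 |

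At n = 318 alone the result runs from 0% to 100%.

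**5. The empty network.** With no edges at all, strength, betweenness and both forms of closeness are 0 for every symptom. No definition of closeness helps there.

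**The case against.** The strongest reply is that the failure needs two things the plan does not state: a sum or mean of distances, and an estimator that produces zero edges. The plan's sentence is a gloss, not a formula, and could be stretched to cover a sum of reciprocals. The sample-size paragraph counts every one of the 435 associations. How the named package treats an unreachable symptom is not in the documents either. All of this stands, and it makes the point conditional. It does not remove it: the plan neither rules out sparsity nor says what to do if a symptom is unconnected, and the sum and mean readings, the more natural ones, both fail.

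Four stronger conclusions might be inferred, and the documents do not support them.

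- *The core-symptom analysis is void.* Only one of three indices is affected, only in a disconnected network. Strength still ranks the linked symptoms.
- *The failure is likely, at some known rate.* The rates above swing with tuning, correlations and group split, and rest on 10 to 40 samples per setting. The graphical LASSO also has no threshold parameters, whereas the plan counts 30, so the simulated model may not be the intended one.
- *The Background shows that some symptoms are rare enough to drop out.* The range "13.75% to 91.5%, which is at a high level" is the incidence of symptom distress across studies, not the prevalence of individual symptoms. The prevalences in the simulations are assumptions.
- *Restricting closeness to linked symptoms makes the groups incomparable, or the zeros would pass as a real difference.* Symptoms linked in both networks can still be compared, and 30 identical zeros would be noticed on inspection. The cost is a rule chosen after seeing the data, and possibly a different set of symptoms in each group.

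**Conclusion.** The point holds conditionally. If the estimator sets edges to zero and a symptom is unconnected in one of the three networks, closeness as 1/(sum or mean of distances) is 0 for 30 of 30 symptoms. It then cannot rank core symptoms in that network or be compared between the long and short dialysis-age groups. With reciprocals summed, 1 of 30 is 0 and the others can be ranked.

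The algebra needs only that unreachable means infinitely distant. How often the condition is met cannot be settled from the documents: it was 0% without sparsity and anywhere from 0% to 100% with it. The case for acting is that the remedy is nearly free, not that the failure is probable. The remedy helps only when a network is partly connected; an empty network is a matter of estimator and sample size.

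**What to change.** In the Statistical Analysis Plan section, replace the verbal description with a formula used identically in all three networks: closeness of a symptom is the sum over the other 29 symptoms of 1/distance, with 0 for any symptom that cannot be reached. Add that unconnected symptoms will be listed for each network. Add that, if a network is empty, the report will say that no centrality index (strength, closeness or betweenness) can name a core symptom in it.

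Naming the edge estimator in the same place would show the reader whether the situation can arise.

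The cost is a few lines in the plan and about one line of code for closeness, with no new data. The downside is that values will not be on the same scale as papers using the older definition. The formula also does not correct for one group's network being sparser because that group is smaller.
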